2. GLOSSARY OF ABBREVIATIONS AND DEFINITION OF TERMS

(e)CRF	(Electronic) Case report form
ADR	Adverse drug reaction
AE	adverse event
AIDS	Acquired immune deficiency syndrome
ALT	Alanine transaminase
AMG	Arzneimittelgesetz (German Drug Act)
ART	Anti-retroviral therapy
AST	Aspartate transaminase
BMD	Bone mineral density
BUN	Blood urea nitrogen
CDC	Centers for Disease Control
E/C/F/TAF	Elvitegravir/Cobicistat/ Emtricitabine/Tenofovir alafenamide
EU	European Union
FDA	(United States) Food and Drug Administration
FDC	Fix-dose combination
Gamma-GT	Gamma-glutamyl transferase
F/TAF	Emtricitabine/Tenofovir alafenamide
GPP	Good Pharmacoepidemiology Practices (guidelines for)
GVP	Good Pharmacovigilance Practices (guidelines for)
HDL	High-density lipoprotein
HIV-1	Human immunodeficiency virus, type 1
ICH	International Conference on Harmonization
IEC	Independent ethics committee
INSTI	Integrase inhibitor
LDL	Low-density lipoprotein
NRTI	Nucleoside reverse-transcriptase inhibitors
PAS	Post-Authorization Study
PASS	Post-Authorization Safety Study
PVE	Pharmacovigilance & Epidemiology
R/F/TAF	Rilpivirine/Emtricitabine/Tenofovir alafenamide
RNA	Ribonucleic acid
SADR	Serious adverse drug reaction
SAE	Serious adverse event
SSR	Special situation report
SUSAR	Serious Unexpected Suspected Adverse Reaction

UACR	Urine albumin/creatinine ratio
UPCR	Urine protein/creatinine ratio
US, USA	United States, United States of America
Analytical dataset	The minimum set of data required to perform the statistical analyses leading to the results of the primary objective(s) of the study
Bias	Systemic error in the design, conduct or analysis of a study that results in a mistaken estimate
Cases	Group of individuals with the condition of interest
Cohort	Group of people characterized by a common experience (eg, occurrence of a specified disease, exposure to a given medication)
Confounder	Extraneous factor that accounts for a difference in disease frequency between the exposure groups; associated factors serving as surrogates for these factors are also commonly called confounders
Confounding by indication	A patient characteristic that is related to the outcome of interest and which influences treatment choice (exposure)
Controls	Group of individuals without the condition of interest but are otherwise similar to cases, or unexposed to or not treated with the agent of interest
Date at which a study commences	Date of the start of data collection
Effect modifier	If an effect measure varies within categories or levels of a variable, that variable is described as an effect-measure modifier
End of data collection	The date from which the analytical dataset is completely available
Exposure	A variable whose effect is of interest and is being studied
External validity	Whether or not the results from the study can be generalized to other populations
Internal validity	Whether or not the study provides an unbiased estimate of what it claims to estimate
Odds	The ratio of the probability that an event will happen to the probability that it will not happen
Outcome	An event (such as disease occurrence or death) that is studied in relation to exposure
Prevalence	Proportion of persons with the exposure/outcome at a specific point in time
Rate	A measure of event occurrence, calculated by dividing the total number of events by the total amount of person-time within an exposure category
Relative Risk (RR)	A general term that can refer to the ratio of 2 risks or the ratio of 2 rates
Risk	The proportion of a fixed cohort in which an outcome occurs during a specified period of time
Start of data collection	Date from which information on the first study subject is first recorded in the study dataset

4. PROTOCOL SYNOPSIS/ABSTRACT

Gilead Sciences GmbH
[name]
[name]
Germany

Title: Non-Interventional Real-Life Study of Effectiveness, Safety, Adherence, and Health-Related Quality of Life in Adult Patients receiving Elvitegravir/Cobicistat/ Emtricitabine/Tenofovir alafenamide (E/C/F/TAF) or Emtricitabine/Tenofovir alafenamide (F/TAF) or Rilpivirine/Emtricitabine/Tenofovir alafenamide (R/F/TAF) for HIV-1 Infection in Germany

Rationale and Background:

Background:

HIV-1 infection remains a life-threatening and serious disease of major public health significance. There are now approximately 35 million people infected worldwide. Globally, incidence continues to grow, with 2.2 million people newly infected with HIV-1 in 2011 alone. The prevalence of people living with HIV-1 infection is also increasing. Patients are being diagnosed earlier, and are living longer due to the success of highly active antiretroviral (ARV) therapy (ART).

Morbidity and mortality of HIV-1 infected patients is increasingly driven by non-AIDS associated comorbidities such as kidney, liver, and heart disease. Even with ART, patients with HIV-1 infection experience more age-related comorbidities, such as renal and bone disease, which manifest earlier than their age-matched HIV-uninfected peers. Moreover, the prevalence and incidence of chronic kidney disease (CKD) and end-stage renal disease (ESRD) is expected to rise as the prevalence of HIV-1 infection continues to rise{22553}.

Current treatment guidelines recommend that patients initiate antiretroviral therapy earlier, thereby requiring lifelong treatment, potentially for 50 years or more. Accordingly, there is a need for new HIV-1 therapies that improve on the current standard of care so that lifelong ART is more effective, more tolerable, and safer for patients.

Tenofovir (TFV) is a nucleotide analog that inhibits HIV-1 reverse transcription. While tenofovir disoproxil fumarate (TDF), an oral prodrug of TFV, is a preferred NRTI for initial therapy, nephrotoxicity is an identified risk, and reductions in bone mineral

density (BMD) have been shown that are larger than those seen with other NRTIs. Tenofovir alafenamide (TAF) is also an oral prodrug of TFV. TAF is more stable in plasma than TDF, provides higher intracellular levels of the active phosphorylated metabolite tenofovir diphosphate (TFV DP), and approximately 90% lower circulating levels of TFV relative to TDF at the clinical doses. These characteristics of TAF are associated with effective suppression of viral replication, and an improved tolerability and safety profile of TAF compared to TDF.

Gilead has coformulated TAF with the HIV-1 integrase inhibitor (INSTI) elvitegravir (EVG; E), the pharmacoenhancer cobicistat (COBI; C), and the NRTI emtricitabine (FTC; F) into a fixed dose combination (FDC) tablet that is suitable for once-daily use. Furthermore Gilead has coformulated TAF with the NRTI emtricitabine (FTC; F) into a fixed dose combination (FDC) tablet for once-daily use with other ARV agents and coformulated TAF with the HIV-1 non-nucleoside reverse transcriptase inhibitor (NNRTI) rilpivirine (RPV; R) and the NRTI emtricitabine (FTC; F) into a fixed dose combination (FDC) tablet for once-daily use. Thus E/C/F/TAF FDC, F/TAF FDC, and R/F/TAF FDC provide potent, convenient, tolerable, and practical regimens for the long-term treatment of patients with HIV-1 infection.

Rationale:

In this non-interventional observational German study we are aiming to describe effectiveness and safety of E/C/F/TAF, F/TAF and R/F/TAF in treatment-naive and treatment-experienced HIV-1 infected adult patients as well as adherence, resource utilization, patient reported outcome data about quality of life, health status, and treatment satisfaction during daily routine use.

Research Question and Objectives:

To describe effectiveness, safety, adherence, resource utilization, and patient reported outcomes of E/C/F/TAF, F/TAF and R/F/TAF use in routine care.

The primary objective of this study is:

- To evaluate HIV-1 RNA and CD4 cell count changes for patients using E/C/F/TAF, F/TAF or R/F/TAF within a time period of 24 months

The secondary objectives of this study are:

- To describe rates adverse drug reactions (ADRs) and serious ADRs (SADRs)
- To describe the motivation for ART initiation in treatment-naïve subjects and factors driving the ART switch to E/C/F/TAF, F/TAF or R/F/TAF in treatment-experienced subjects
- To describe adherence and reasons for E/C/F/TAF, F/TAF or R/F/TAF discontinuation during the study
- To describe physical and mental health-related quality of life, health status, and treatment satisfaction using standardized questionnaires Health Survey Short Form (SF-36), HIV Symptom Index, and HIV Treatment Satisfaction Questionnaire
- To describe health care resource utilization (eg, number of hospitalizations, number of physician visits)

The above parameters will be evaluated in the overall cohort and in various subgroups (eg, treatment-naïve subjects versus treatment-experienced subjects, age (< 50 years, ≥ 50 years), presence of specific comorbidities, sex).

The collection of ADR/SADR reflects the real-life situation, in which the treating physician with best knowledge of his patient assesses whether an observed event could be related to a given treatment. In this way, the study will collect safety data that is reflective of the real-life setting in which it is conducted.

Study Design:

Prospective, non-interventional, observational cohort study. Enrolled subjects will be documented using an electronic case report form (eCRF) by the participating sites. Each enrolled subject will be followed for 24 months (irrespective of regimen changes).

Population:

The study will enroll 900 adult (age ≥ 18) treatment-naïve and treatment-experienced HIV-1 infected subjects initiating treatment with E/C/F/TAF, F/TAF or R/F/TAF in routine care.

E/C/F/TAF arm: 150 treatment-naïve and 150 treatment-experienced subjects, at least 20% of the total 300 subjects will be ≥ 50 years of age at enrollment

F/TAF arm: 150 treatment-naïve and 150 treatment-experienced subjects, all 150 treatment-experienced subjects will be ≥ 50 years of age at enrollment

R/F/TAF arm: 150 treatment-naïve and 150 treatment-experienced

subjects, at least 20% of the total 300 subjects will be ≥ 50 years of age at enrollment

Participating study sites (hospitals and private practitioners) are specialized on treating HIV patients. All study sites are located in Germany.

Variables:

Prior to E/C/F/TAF, F/TAF or R/F/TAF treatment initiation (baseline):

Gender, year of birth, body weight and height

Race

Date of HIV-1 diagnosis

CDC stage

Co-morbidities as available from medical records

Laboratory parameters as available from medical records:

- HIV-1 RNA and limit of detection of the used assay
- CD4 cell count
- AST, ALT, gamma-GT
- Albumin
- Urine albumin/creatinine ratio (UACR), urine protein/creatinine ratio (UPCR)
- Serum total protein
- Triglycerides
- Total cholesterol
- HDL, LDL
- Serum glucose
- Serum phosphate
- Serum creatinine
- Serum uric acid
- Blood urea nitrogen (BUN)
- Calcium, chloride, magnesium, potassium, sodium
- Urine dipstick parameters (glucose, leukocytes, nitrite, protein, pH, ketone bodies)
- Urine quantitative protein, albumin, and creatinine

- Hematology profile (complete blood count with differential and platelet count)
- Bone mineral density

History of anti-retroviral therapy

CD4 nadir

Blood pressure

Historic serum creatinine, quantitative urine creatinine, quantitative urine albumin, quantitative urine protein, and body weight within the last 2 years prior to E/C/F/TAF, F/TAF or R/F/TAF treatment initiation

Co-medications as available from medical records

Resistance status as available from medical records

Motivation for ART initiation in treatment-naïve subjects and factors driving the ART switch to E/C/F/TAF, F/TAF or R/F/TAF in treatment-experienced subjects

Cardiovascular and renal risk factors (family history of angina/heart attack, smoking status, intravenous drug use, prior use of atazanavir, tenofovir disoproxil fumarate (TDF), indinavir or lopinavir)

HIV Symptom Index

HIV Treatment Satisfaction Questionnaire (only for treatment-experienced subjects)

SF-36

During follow-up (approximately 3 months, 6 months, 12 months, 18 months, and 24 months after starting E/C/F/TAF, F/TAF or R/F/TAF therapy):

Anti-retroviral therapy adherence (VAS scale and number of missed doses during the last 4 and 30 days)

In case of E/C/F/TAF, F/TAF or R/F/TAF discontinuation: date and reason for discontinuation and new ART (patients will be documented up to 24 months even after therapy switch)

Changes in co-medications as available from medical records

Body weight

Laboratory parameters: see baseline

New AIDS-defining events (CDC class C, excluding CD4 cell count < 200 cells/ μ L)

New co-morbidities/co-infections

ADRs and SADR

Special situations reports as appropriate

Only approximately 12 months and 24 months after starting E/C/F/TAF, F/TAF or R/F/TAF therapy:

Blood pressure and cardiovascular and renal risk factors (eg, family history of angina/heart attack, smoking status, intravenous drug use)

HIV Symptom Index

HIV Treatment Satisfaction Questionnaire (only for treatment-experienced subjects approximately 3 months, 6 months, and 12 months after starting E/C/F/TAF, F/TAF or R/F/TAF therapy)

SF-36

In case of virologic failure: resistance status as available

Health care resource utilization (number and duration of hospitalizations, number of appointments with HIV-treating physician and with other physician types)

Data Sources:

Collection of routine visit data and questionnaires via eCRF

Study Size:

The study will enroll 900 adult (age \geq 18) treatment-naive and treatment-experienced HIV-1 infected subjects initiating treatment with E/C/F/TAF, F/TAF or R/F/TAF in routine care. Each study arm will enroll 150 treatment-naive and 150 treatment-experienced subjects.

- Data Analysis:** For categorical variables, numbers and percentages of patients will be reported including according 95% confidence intervals.
- For continuous variables, mean, standard deviation (SD), minimum, first and third quartile (Q1, Q3), median, and maximum will be calculated, together with the total number of observations and the number of missing values.
- Descriptive statistics will summarize demographics and baseline characteristics (including the type of regimen at enrollment).
- The questionnaires scores will be calculated according to the algorithms elaborated for these questionnaires.
- Visit windows will be defined (in the statistical analysis plan) to group data in order to generate descriptive statistics across time to assess potential trends in patient reported outcome questionnaires, safety data or CD4. P-values and/or confidence intervals (95% two-sided) will be calculated when considered relevant.
- Multivariate analyses will be conducted to compare the treatment-naïve and non-naïve treatment groups in each arm to estimate adjusted rates and proportions. Longitudinal analysis will be done using mixed models.
- Milestones:** Start of data collection : January 2016
End of Data collection: 4th quarter 2019
Final Study report: 3rd quarter 2020
-

This study will be conducted in accordance with the guidelines of Good Pharmacoepidemiology Practices (GPPs) and Heads of Medicines Agencies (HMA) Good Pharmacovigilance Practices (GVP) including archiving of essential documents.

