9. RESEARCH METHODS

9.1. Study Design

This non-interventional study does not influence the treatment decisions made by the participating physicians. Subjects can be enrolled in this study after the physician has decided to treat a specific subject with E/C/F/TAF, F/TAF or R/F/TAF in accordance with the approved respective SmPCs. All treatments will be prescribed according to local treatment guidelines and/or routine clinical practice. The treating physician will make all treatment decisions and will provide prescriptions for his/her patients. There will be no study-specific procedures.

The study is designed as a multicenter, non-interventional observational cohort study, in accordance with the German Drug Act (§63f AMG). It is planned to enrol a total of 900 adult (age ≥ 18) HIV-1 infected subjects initiating treatment with E/C/F/TAF (n=300), F/TAF (n=300) or R/F/TAF (n=300) in routine care. The study will enroll approximately 150 treatment-naïve and 150 treatment-experienced subjects in each arm.

Data collection will be performed by manual entry of data from the patient's medical file and questionnaires to a computer-based electronic case report form (eCRF). No patient initials will be included.

Data will be prospectively collected for each enrolled subject for approximately 24 months. In case of E/C/F/TAF, F/TAF or R/F/TAF discontinuation the date of discontinuation, reasons for discontinuation (eg, patient wish, adverse reaction, insufficient efficacy) and subject's new ART will be collected. The subject will remain in the study and will be continuously documented with the new ART until premature end of documentation (eg, due to lost to follow up) or until reaching the defined end of documentation approximately 24 month after enrollment.

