9.7. Data Analysis

Data will be analysed per arm. For categorical variables, numbers and percentages of patients will be reported including the according 95% confidence intervals.

For continuous variables, mean, standard deviation (SD), minimum, first and third quartile (Q1, Q3), median, and maximum will be calculated, together with the total number of observations and the number of missing values.

Missing values will not be imputed but classified as an own category to keep them for multivariate analyses.

Descriptive and multivariate data analysis will be done per treatment arm. Some cross arm comparisons according to sub groups (age \geq 50 years) might be conducted depending on group size.

Descriptive statistics will summarize demographics and baseline characteristics (including the type of regimen at enrollment).

The questionnaires scores will be calculated according to the algorithms elaborated for these questionnaires.

Visit windows will be defined (in the statistical analysis plan) to group data in order to generate descriptive statistics across time to assess potential trends in patient reported outcome questionnaires, safety data or CD4. P-values and/or confidence intervals (95% two-sided) will be calculated when considered relevant.

Multivariate analyses per arm (logistic regression) will be conducted to compare treatment naïve and non-naïve treatment groups adjusting for covariates. Longitudinal analysis will be done using mixed models.

Demographics and baseline measures would be potential confounders/effect modifiers for multivariate analyses. Confounders/effect modifiers and respective adjustments will be addressed in the Statistical Analysis Plan.

ADRs/SADRs and comorbidities will be coded using the Medical Dictionary for Regulatory Activities (MedDRA).

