1.1 Does the protocol specify timelines for				
1.1.1 Start of data collection ¹				16
1.1.2 End of data collection ²				16
1.1.3 Study progress report(s)				
1.1.4 Interim progress report(s)				
1.1.5 Registration in the EU PAS register				16
1.1.6 Final report of study results.				16

Comments:

--

Section 2: Research question	Yes	No	N/A	Page Number(s)
2.1 Does the formulation of the research question and objectives clearly explain:				
2.1.1 Why the study is conducted? (e.g. to address an important public health concern, a risk identified in the risk management plan, an emerging safety issue)				17, 18
2.1.2 The objective(s) of the study?				19
2.1.3 The target population? (i.e. population or subgroup to whom the study results are intended to be generalised)				20, 21
2.1.4 Which formal hypothesis(-es) is (are) to be tested?				
2.1.5 If applicable, that there is no a priori hypothesis?				

¹ Date from which information on the first study is first recorded in the study dataset or, in the case of secondary use of data, the date from which data extraction starts.

² Date from which the analytical dataset is completely available.

Comments:

No formal hypothesis testing, comparisons between various subgroups will be done using logistic or longitudinal models.

Section 3: Study design	Yes	No	N/A	Page Number(s)
3.1 Is the study design described? (e.g. cohort, case-control, randomised controlled trial, new or alternative design)				20

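### The synopsis promises adjusted rates for the naïve versus experienced comparison, but the model Section 9.7 names for it, logistic regression, uses no person-time and cannot give a rate as the glossary defines it

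*Protocol*

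**What the plan says.** The Data Analysis part of the synopsis (Section 4) gives the purpose of the naïve versus experienced models: "Multivariate analyses will be conducted to compare the treatment-naïve and non-naïve treatment groups in each arm to estimate adjusted rates and proportions".

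Section 9.7 gives the method for the same comparison: "Multivariate analyses per arm (logistic regression) will be conducted to compare treatment naïve and non-naïve treatment groups adjusting for covariates". Its next sentence names the only other model: "Longitudinal analysis will be done using mixed models". The comment under Section 2 of the ENCePP checklist (Annex 2) agrees, stating that "comparisons between various subgroups will be done using logistic or longitudinal models". No count model, person-time offset or time-to-event model is named anywhere.

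The glossary (Section 2) separates two quantities. A rate is "A measure of event occurrence, calculated by dividing the total number of events by the total amount of person-time within an exposure category". A risk is "The proportion of a fixed cohort in which an outcome occurs during a specified period of time".

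Section 8 makes ADR/SADR rates a secondary objective, lists numbers of hospitalizations and physician visits as another, and says these parameters will be evaluated by subgroup, including naïve versus experienced. Follow-up is planned as about 24 months for everyone, including after a regimen switch, but Section 9.1 lets it run only "until premature end of documentation (eg, due to lost to follow up", among other possible reasons. Under Section 11.4, ADR reporting stops at the earliest of several events, one of them four weeks after study drugs are stopped.

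**The concern.** The synopsis states an output and Section 9.7 states a tool, and on the glossary's terms the tool cannot produce half of that output. A logistic model takes one yes/no result per subject. It can give adjusted proportions, but time at risk does not enter it, so it cannot give events per unit of person-time.

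This bears on outcomes that accrue over follow-up. If subjects are classed as having had at least one ADR or admission, someone documented for 3 months without an event counts the same as someone documented for 24 months without one. If naïve and experienced subjects also leave documentation at different speeds, the adjusted contrast partly measures how long each group was watched. A statistical analysis plan that follows Section 9.7 literally would not meet the synopsis, and one that adds a rate model would go beyond Section 9.7.

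**Working it through.** **Text check.** By the glossary, an adjusted rate needs events and person-time. Logistic regression uses no person-time. Mixed models are assigned to longitudinal analysis, with no count outcome or offset mentioned. Section 9.7 defers confounders and adjustments to the statistical analysis plan, but it names the model for this comparison itself. The mismatch is therefore in the protocol and is not just a detail left open.

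**Size.** The protocol has no figure of its own to reproduce here: it gives no ADR rate, admission rate, dropout rate or expected follow-up gap. All inputs below are assumptions, except the group size of 150 versus 150 (Section 9.1) and the 24-month plan. Each subject is treated as observed for the group's mean time, with a constant event rate.

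With rate r and observed time T in years:
- probability of at least one event: p = 1 − exp(−rT)
- odds: p/(1 − p) = exp(rT) − 1
- odds ratio seen by a model ignoring T: [exp(rT₁) − 1]/[exp(rT₂) − 1]

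Take the same rate in both groups, T₁ = 18/12 = 1.5 and T₂ = 22/12 = 1.833:
- r = 0.3: p₁ = 1 − exp(−0.45) = 36.2%; p₂ = 1 − exp(−0.55) = 42.3%; odds ratio = 0.568/0.733 = 0.775, that is 0.78
- r = 0.1: odds ratio = 0.162/0.201 = 0.80
- r = 1.0: odds ratio = 3.482/5.255 = 0.66

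The true rate ratio is 1.00 throughout. At r = 0.3 the expected events per subject are 0.45 and 0.55. Divided by 1.5 and 1.833 years, both return 0.30, which is what an offset for log time does.

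**Second set of assumptions**, with the longer-observed group in the numerator. The last column is the share of 200,000 simulated 150-versus-150 comparisons declared different by a two-sided 5% Wald test:

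| Rate per year | Months observed | At least one event | Odds ratio | Declared different |
|---|---|---|---|---|
| 0.10 | 24 vs 24 | 18.1% vs 18.1% | 1.00 | 5% |
| 0.10 | 24 vs 21.6 | 18.1% vs 16.5% | 1.12 | 6% |
| 0.10 | 24 vs 18 | 18.1% vs 13.9% | 1.37 | 16% |
| 0.30 | 24 vs 18 | 45.1% vs 36.2% | 1.45 | 36% |
| 0.10 | 24 vs 12 | 18.1% vs 9.5% | 2.11 | 58% |

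The distortion is nil with equal observation, small with a gap of 2.4 months, and material from about 6 months.

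**The case against.** The strongest reply is that *rates* in the synopsis may simply mean percentages. Section 9.5 uses the word that way for viral suppression, and the glossary is a general list that also defines terms such as cases and controls. On that reading logistic regression supplies what was promised and only the wording is loose. This stands as a possibility. It does not remove the conflict with the glossary, and it leaves the ADR and resource-use objectives without an adjusted rate model.

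Other points also stand. Section 9.7 assigns no outcome to the logistic model, and the ADR and resource-use objectives are descriptive. A reader might infer that admissions will be reduced to yes/no and repeat admissions discarded, but the protocol does not say so. The 24-month plan, kept after switching, limits any gap in observation time, and the checklist says there is no formal hypothesis testing.

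A reader might also infer that the study will report odds ratios that exaggerate small differences in viral suppression. The documents do not support that. They do not commit to odds ratios, the checklist marks measures of effect as not applicable, and the synopsis already promises adjusted proportions, which a logistic fit can supply.

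**Conclusion.** The mismatch holds as a matter of text: the synopsis promises adjusted rates, and the model named for the comparison cannot produce them as the glossary defines them.

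The consequence is conditional. Equal rates can appear different only if logistic regression is applied to events accruing over time and the two groups are observed for different lengths of time. With an assumed equal rate of 0.3 per person-year and 18 versus 22 months, the odds ratio is 0.78, and it runs from 0.80 to 0.66 across rates of 0.1 to 1.0. With equal observation it is 1.00. The documents do not support the stronger statement that the planned analysis will bias these comparisons, because they give neither event rates nor a follow-up gap. The point affects secondary comparisons, is cheap to correct and should be corrected.

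**What to change.** Align the synopsis with Section 9.7:

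- **Event rates.** For adjusted comparisons of ADRs/SADRs, hospitalizations and appointments, use negative binomial or robust Poisson regression. Report adjusted rates and rate ratios with 95% confidence intervals.
- **Offset.** Use the log of the time over which that event type was actually captured. One total documentation time will not do for all. For ADRs/SADRs it is the reporting period of Section 11.4. For hospitalizations and other-physician appointments, which Section 9.4 takes from patient questionnaires, it is the periods covered by returned questionnaires. For visits at the study site it is documented site time.
- **Proportions.** Keep logistic regression for outcomes at fixed time points, such as HIV-1 RNA < 50 copies/mL, and report the adjusted proportions the synopsis already promises.
- **Wording.** If percentages were meant, delete *rates* from the synopsis sentence, and still use the count model for any adjusted comparison of event rates.

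The cost is wording and programming, with no new data items. Capture time must be derived for each event type, and rare outcomes such as SADRs will support few covariates.
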